2. PROJECT SUMMARY

We propose to evaluate the efficacy of a CAA-based intervention to change alcohol-related attitudes in support of moderate drinking. Specifically, heavy-drinking college students will be prompted to advocate for a counter-attitudinal topic (i.e., benefits of avoiding problems) by responding to a prompt asking them to detail how to avoid negative consequences by using self-generated protective behavioral strategies (PBS) and why this is a beneficial approach to drinking. With the understanding that their responses will inform future prevention programs, participants will then review their statements publicly with a research assistant. The new CAA intervention will be compared to (a) an assessment only (AO) control to determine absolute efficacy, and to (b) an empirically-supported personalized normative feedback (PNF)

intervention to determine relative efficacy, using a non-inferiority design. This study evaluates a novel intervention protocol linked to a clearly defined mechanism of behavior change and grounded in basic psychological research. If found to be efficacious, or at least non-inferior to the established PNF, the CAA approach will advance prevention science by targeting a separate and unique mechanism of change, and it will add to the toolbox of strategies available to colleges and universities to prevent harms related to drinking.

3. STUDY RATIONALE

College students drink more and experience more consequences than their same-age, non-college peers (White & Hingson, 2014). Brief prevention interventions developed for college drinkers have effectively reduced alcohol use and consequences, with small-medium effects (Carey, Scott-Sheldon, Carey, & DeMartini, 2007; Carey, Scott-Sheldon, Elliott, Garey, & Carey, 2012; Samson & Tanner-Smith, 2015; Scott-Sheldon, Carey, Elliott, Garey, & Carey, 2014). Notably, mechanisms of change targeted by these interventions have been dominated by perceived descriptive norms (Reid & Carey, 2015). The strong emphasis on normative feedback as a core mechanism of change may have contributed to a dearth of attention to alternative paradigms. To this point, research consistently demonstrates associations between attitudes toward drinking and drinking behavior (Collins & Carey, 2007; Huchting, Lac, & LaBrie, 2008; Stacy, Bentler, & Flay, 1994), and attitudes have been shown to be stronger predictors of drinking than norms ([name], Miller, [name], Reid & Carey, 2018).

Although attitudes are a key element of many health behavior models (Montano & Kasprzyk, 2008), they are rarely directly targeted in individually-focused alcohol interventions. Attitudes are defined as evaluative judgments that can range from negative to positive and are subject to situational influences and observations of one's own behavior (Bem, 1967; Higgins, 1987). The present research adapts a classic attitude-change paradigm (counter-attitudinal advocacy, or CAA), which has been used widely and successfully in other domains such as smoking cessation (e.g., Simmons, Heckman, Fink, Small, & Brandon, 2013), for use in alcohol prevention. With CAA, individuals who voluntarily endorse a specific position (e.g., disapproval of heavy drinking), that is discrepant from their current attitude and/or behavior, come to change their attitude and/or behavior in the direction of the endorsed position. This approach is particularly effective when the professed attitude is public, self-generated, and internally motivated. (Kim, Allen, Preiss, & Peterson, 2014), and the current procedure incorporates all these elements. An advantage of the CAA approach to promoting change in drinking behavior is that participants self-generate risk reduction plans without having to self-identify as wanting to change, which is an advantage for use in prevention programs.

4. AIMS AND ENDPOINTS

Aim 1. Examine the effects of CAA on alcohol outcomes. Our primary hypothesis is that, relative to AO control, the CAA intervention will (a) increase positive moderate drinking attitudes, (b) decrease positive heavy drinking attitudes, (c) increase attitude-behavior dissonance, and (d) decrease drinks per drinking day, binge frequency, peak BAC, and alcohol consequences, and increase the use of PBS.

Aim 2. Compare the effects of CAA vs. PNF. A secondary hypothesis is that CAA will be no less efficacious than (i.e., not inferior to) PNF in reducing alcohol outcomes as measured by alcohol consumption and alcohol related consequences.

Aim 3. Test specific theory-based mediational pathways. Aim 3a. We predict that the effects of the CAA intervention on alcohol consumption and consequences will be mediated by increases in (a) positive attitudes towards moderate drinking and (b) dissonance (but not perceived norms). Aim 3b. We predict that the effects of the PNF intervention on alcohol

consumption and consequences will be mediated by decreases in (a) perceived descriptive norms and (b) dissonance (but not attitude change).

Aim 4. Test intervention-specific moderators of outcome. Aim 4a. We predict that the effect of the CAA intervention will be enhanced by stronger drinker identity, greater need for consistency, and will not differ by study site. Aim 4b. We predict that response to the PNF condition will be enhanced by weaker drinker identity, greater need for consistency, and will be stronger within a lighter drinking community (the Houston site).

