9.1.4. Hypothesized mediators

Attitudes toward moderate consumption and attitudes toward heavy consumption will be assessed with measures modified from previous research (Hagger et al., 2012; Norman, 2011). For moderate consumption, the stem will read, "Keeping my alcohol drinking within what is considered moderate drinking for adults (i.e. at 4 or fewer drinks for men or at 3 or fewer drinks for women) on each individual occasion over the next month would be..." For heavy consumption, the stem will read, "Having five or more drinks (for males)/four or more drinks (for females) in a sitting over the next month would be..." For both measures, there are five semantic differential scales that range from 1 to 5: unenjoyable-enjoyable, bad-good, harmful-beneficial, foolish-wise, and unpleasant-pleasant. To test AIM 3, changes in attitudes toward heavy drinking and attitudes toward moderate drinking are anticipated to serve as a mediator of the CAA (but not PNF) intervention effects.

Cognitive dissonance will be assessed using the Dissonance Thermometer (Devine, Tauer, Barron, Elliot, & Vance, 1999; Elliot & Devine, 1994; Simmons & Brandon, 2007; Simmons et al., 2004; Simmons, et al., 2013). Items include asking participants how uncomfortable, angry at themselves, shameful, uneasy, friendly (reverse scored), disgusted with themselves, embarrassed, bothered, optimistic (reverse scored), annoyed at themselves, disappointed at themselves, happy (reverse scored), energetic (reverse scored), and good (reverse scored) they feel immediately following the CAA activity. The 3-item affective discomfort factor has been found to be susceptible to cognitive dissonance inductions resembling our CAA procedure, with other target behaviors (Devine et al., 1999; Simmons et al., 2013). In Aim 3 we will test dissonance as a mediator of both CAA and PNF interventions.

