Perceived descriptive norms will be measured by a modified version of the Drinking Norms Rating Form (DNRF; Baer et al., 1991). The gender-specific version (Lewis & [name], 2004) assesses perceived typical number of drinks consumed per drinking occasion (e.g., "how many drinks on average do you think a typical male/female Brown/UH student consumes on a given occasion?"), and perceived frequency of drinking occasions (e.g., "how often do you think a typical male/female Brown/UH student consumes alcohol?"). The DNRF assesses perceived typical weekly drinking by having participants fill in the average number of standard drinks they think the typical (male/female) Brown/UH student consumes for each day of the week over the previous month. The DNRF has been used in multiple studies of college drinking and has shown good concurrent and prospective validity ([name], Dillard, Lewis, Bergstrom, & Neil, 2006). In Aim 3 we test changes in descriptive norms as mediators of the PNF (but not CAA)

effects.

Perceived Injunctive norms will also be assessed using an adaptation of the DNRF shown to be reliably associated with respondent drinking (Krieger et al., 2016). This drink-based injunctive norms assessment includes (a) “maximum number of drinks a typical male/female Brown/UH student approves of consuming on one occasion?”, (b) “maximum frequency of drinking a typical male/female Brown/UH student would approve of in a week?”, and (c) “what is the maximum number of drinks a typical male/female Brown/UH student would consider acceptable to consume on each day of the week?.” [name] et al. (in preparation) recently demonstrated support for personalized injunctive norms feedback based using this measure (see preliminary studies). Additionally, injunctive norms will be assessed for negative consequences of drinking. Rating scales will be used to assess how unacceptable and acceptable experiencing specific drinking consequences is believed to be (Prince et al., 2015). These consequences include driving after drinking, drinking enough to pass out, blacking out due to drinking, etc. In Aim 3 we test changes in injunctive norms as mediators of the PNF (but not CAA) effects.

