10. STATISTICAL CONSIDERATIONS

10.1. Sample Size. Power analyses focus on estimating a sample size large enough to detect “true” effects, thereby avoiding Type II errors. Sample size estimates were obtained for intervention contrasts. Necessary sample sizes were assessed via sample size and power equations for multi-level models using the Optimal Design software program. Based on previous findings using CAA and PNF approaches, we anticipate intervention effects relative to the neutral control condition to be in the small to medium range but at least comparable to effects which have been reported for personalized normative feedback, which are typically in the .28 range (e.g., Dotson et al., 2015). Based on the proposed sample size of 600, given four assessment points, we anticipate the ability to detect effects of intervention contrasts and moderation effects across the small to medium range. Considering maximum anticipated attrition rates of 15% (N=510) we will have .70, .80, and .90 power to detect effects sizes of $\delta = .24, .27, \text{ and } .32$, respectively.

10.2. Analysis Plan. Aims will be evaluated using generalized linear mixed models, an extension of general linear models allowing for multi-level data with non-normal distributions (e.g. Atkins, Baldwin, Zheng, Gallop, & [name], 2013; Hedeker & Gibbons, 2006). With respect to evaluating main effects of experimental conditions on drinking, each participant will provide up to four assessments (baseline, 1-month, 3-month, and 6-month follow-up data). Hypotheses will be tested using specific contrast vectors, using a general linear hypothesis framework (Fox, 2008).

Hypotheses associated with Aim 1 will be evaluated examining outcomes as a function of two dummy coded variables representing CAA and PNF with control as the reference group. Time X CAA outcomes will provide direct tests of differences in change between CAA and control groups. We will utilize a Bonferroni correction with Šídák adjustment for correlated outcomes to reduce alpha inflation associated with multiple outcomes (i.e., moderation attitudes, heavy drinking attitudes, dissonance, drinks per drinking day, binge frequency, peak BAC, alcohol consequences, and PBS use).

For these analyses, each participant will provide up to 4 repeated measures (i.e., baseline, 1-month, 3- months, 6-months), yielding up to 2400 Level 1 cases (repeated-measures) across 600 Level 2

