Hypotheses associated with Aim 3 will evaluate mediators of intervention effects. We will follow procedures described by MacKinnon and colleagues (e.g., MacKinnon, Fairchild, & Fritz, 2007) to assess mediation. Mediation will test indirect effects using the AB products method with bootstrapped standard errors where A will represent effects of intervention contrasts by time interactions on mediators. B will represent the associations of mediators on subsequent drinking outcomes. Both A and B paths will control for baseline outcomes. Hypotheses associated with Aim 4 will follow a similar approach but will add prospective moderators and products of prospective moderators and contrasts

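### Aim 3 predicts mediation through some mechanisms but not others, while section 10.2 tests only individual indirect effects, so the selective part of the prediction has no test

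*Combined protocol and SAP*

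**What the plan says.** Section 4 makes two selective predictions. Under Aim 3a, the effects of CAA on consumption and consequences "will be mediated by increases in (a) positive attitudes towards moderate drinking and (b) dissonance (but not perceived norms". Under Aim 3b, the effects of PNF are to be "mediated by decreases in (a) perceived descriptive norms and (b) dissonance (but not attitude change".

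Section 9.1.4 repeats the selectivity as a comparison of arms for a given mediator. Changes in attitudes to both heavy and moderate drinking are "anticipated to serve as a mediator of the CAA (but not PNF) intervention effects". Descriptive norms are assigned the opposite way, and for injunctive norms the text reads: "In Aim 3 we test changes in injunctive norms as mediators of the PNF (but not CAA) effects".

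The mediation method is one short paragraph in section 10.2. It says "Mediation will test indirect effects using the AB products method with bootstrapped standard errors", defines A as the intervention-by-time effect on the mediator and B as the mediator's association with later drinking, and adds "Both A and B paths will control for baseline outcomes". It states no comparison of indirect effects between mediators or between arms, no bound for calling a pathway absent, and no choice between fitting mediators singly or jointly.

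**The concern.** Each Aim 3 prediction has a positive half (these pathways carry the effect) and an excluding half (that one does not). Testing each AB product against zero addresses the positive half only. The excluding half would have to be read from a non-significant result, which is also what low power produces. A contrast between a significant and a non-significant product is not a test of their difference.

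At stake is the mechanism conclusion. CAA could be reported as working through attitudes and not norms when it works equally through both. Aims 1 and 2 are unaffected.

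**Working it through.** **The plan's own figure.** The only power statement (section 10.1, repeated in item 13 of the Data and Safety Monitoring Plan) is .70, .80 and .90 at δ = .24, .27 and .32 with N = 510, or 170 per arm. A two-group comparison of means at one-sided 5% gives .715, .801 and .904. Two-sided 5% on a single measure gives .600, .702 and .839. Two-sided 5% on the mean of four measures with an assumed within-person correlation of .72 gives .702, .800 and .913. The figure can therefore be reproduced, but it concerns intervention contrasts. No power is given for mediation, so power per mediator (p) is left free below.

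**Chance of the predicted split when the mediators are equal.** Assume equal non-zero indirect effects, each detected with power p, and independent tests.

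- One predicted and one excluded mediator: p(1−p).
- Full Aim 3a pattern (attitudes and dissonance significant, norms not): p²(1−p).
- The same, with descriptive and injunctive norms both required to be non-significant: p²(1−p)².

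| p | One pair | Full Aim 3a | Both norms excluded |
|---|---|---|---|
| .20 | .160 | .032 | .026 |
| .30 | .210 | .063 | .044 |
| .50 | .250 | .125 | .0625 |
| .67 | .222 | .148 | .049 |
| .80 | .160 | .128 | .026 |

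The maxima are .25 at p = .50, 4/27 = .148 at p = 2/3, and .0625 at p = .50. They do not depend on the significance level. Obtaining the full Aim 3a and 3b patterns together has a maximum of (4/27)² = .022.

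**Correlated tests.** The products share participants, arm contrast and outcome, so independence is only a reference case. For bivariate normal test statistics with correlation r and p = .5, the pair probability is 1/4 − arcsin(r)/(2π). This gives .202 at r = .3, .167 at r = .5 and .315 at r = −.4. The corresponding maxima for the three-part pattern are .112, .089 and .215.

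**No mediation at all.** At p = .05 the pair rate is .05 × .95 = .0475 and the three-part rate is .05² × .95 = .0024. The problem is confined to equal, non-zero mediators.

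**Simulation.** Settings: 170 versus 170, three equal mediators, and a mediator called significant when the lower limit of its 95% interval exceeded zero. A Monte Carlo interval stood in for the bootstrap, with 1,000 runs per scenario. Assumed values were A = .20 to .30 SD, B = .30 and mediator correlation 0 to .5, with mediators fitted singly and jointly. The false pair split occurred in 9.7% to 25.4% of runs and the false three-part pattern in 5.8% to 14.8%. When the 95% interval for the difference also had to lie above zero, the pair rate fell to 1.1% to 3.2%. With both predicted mediators significant and both required to exceed norms in this way, the rate was 0.1% to 0.8%.

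**The case against.** The strongest reply is that the exclusions are predictions, and that no section says selectivity will be declared from a significant/non-significant split. Section 10.2 also says "Hypotheses will be tested using specific contrast vectors, using a general linear hypothesis framework", which could cover a comparison of indirect effects. The first part is fair: the rule is inferred because no other is given. The second does not fill the gap. The statement is general, no contrast of indirect effects is specified, and the contrasts named in the Aim 3 paragraph define the A path. The multiplicity correction is stated for Aim 1 outcomes and would not test a difference in any case.

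Three stronger readings are tempting, and the documents do not support them.

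- A reader might infer that the Aim 3a pattern can arise by chance one time in four. That maximum belongs to a single pair at 50% power with independent tests; the stated prediction has three parts.
- A reader might infer that, because section 9.1.4 adds heavy-drinking attitudes and injunctive norms, any convenient pair could be chosen afterwards. That section gives every measure a fixed direction, and section 4 words its exclusions broadly. What remains open is narrower: which measures must be non-significant for an exclusion to count.
- A reader might infer that selectivity is the trial's headline conclusion. Section 2 ties its remark about a distinct mechanism to CAA being efficacious or non-inferior, and section 4 labels Aim 1 primary and Aim 2 secondary but gives Aim 3 neither label.

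**Conclusion.** The concern holds for the interpretation of Aim 3. The plan predicts selective mediation and specifies no analysis that can support it. With equal non-zero mediators and independent tests, the misleading split has a maximum probability of 25% for one pair, about 15% for the full Aim 3a pattern, and about 6% if both norm measures must be non-significant. These are maxima over an unknown power. They fall with positive correlation between tests and rise with negative correlation (pair maximum about .17 at r = .5 and .32 at r = −.4). With no mediation through any route, the pair rate is about 5% or less.

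A significant difference would not by itself justify an exclusion claim either: norms could carry a material effect that is merely smaller than that of attitudes.

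**What to change.** In section 10.2 (Aim 3), add participant-level bootstrap confidence intervals for:

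1. The within-arm difference of indirect effects on the same outcome, with pairs named in advance. For CAA: moderate-drinking attitudes minus descriptive norms, and minus injunctive norms. For PNF: descriptive norms minus moderate-drinking attitudes, and minus heavy-drinking attitudes.
2. The CAA-versus-PNF difference in indirect effect for the same mediator, which is the form of the predictions in section 9.1.4.

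State the reporting rule with them. If a difference interval excludes zero, conclude only that more of the effect runs through one mediator than the other, or through that mediator in one arm than in the other. Say that a pathway is not involved only if its own interval also lies within a pre-specified negligible bound. Otherwise report the indirect effects with their intervals and make no specificity claim.

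The cost is analysis-plan text, a justified bound, and contrasts computed from bootstrap samples already planned; no new data are needed. The downside is that a specificity claim becomes harder to make.

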5. STUDY DESIGN

We will use a multi-site randomized controlled trial (RCT) to evaluate the effects of counter attitudinal advocacy (CAA) relative to assessment only (AO) control on drinking and related problems among college students, and the relative effects of CAA vs. PNF on relevant drinking outcomes. Eligible students will be randomly assigned to one of 3 conditions (personalized CAA or PNF or AO control). Hypothesized mechanisms of change (alcohol-related attitudes and dissonance, perceived drinking norms) will be evaluated immediately after the intervention (posttest) and drinking outcomes (drinks per week, heavy drinking frequency, peak BAC, alcohol-related problems, PBS) will be evaluated at 1-, 3-, and 6-months post-intervention. All procedures are conducted for the purpose of research only.

We propose to conduct this study at two sites (both Carnegie Tier 1 Research universities) that have distinctly different campus and student profiles in order to explicitly test hypotheses about the differential efficacy of CAA vs PNF in different campus contexts. Brown University is a private residential 4-year college with approximately 6200 undergraduates (51% female and 43% minority) and characteristics associated with higher risk of alcohol misuse (e.g., Northeast region, Greek system, athletic tradition). All first- and second-year students and most third-year students live together in on-campus dorms. Students at Brown report high rates of drinking: 81% of Brown students drank in the past 3 months, and 51% report binge drinking in the last two weeks. In contrast, the University of Houston (UH) is a large public research university serving more than 34,716 undergraduate students (51% female and 74% minority). Roughly 80% of UH students live off campus. Located in America's fourth-largest city, UH was designated as the most ethnically diverse metropolitan research university in the United States by Forbes in 2010. UH students report a below average drinker profile, with 45% of the students reporting current drinking and 23% report binge drinking in the last month. Overall, the base rates for any drinking and binge drinking are lower at UH than at Brown. These two sites allow us to test the comparative efficacy of CAA vs PNF in contexts with both high and low base rates of heavy drinking. If site does not moderate efficacy, then the replication of the effects of CAA across sites will provide evidence of generalizability of observed effects.

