6. STUDY POPULATION

6.1. Target Sample. The target sample for analyses is $N=600$ college student drinkers: 300 from Brown University, and 300 from the University of Houston. We will randomize 100 eligible students from each site to the CAA ($n=200$), PNF ($n=200$), and AO ($n=200$) conditions.

6.2. Inclusion Criteria. Inclusion criteria are:

(1) **Age 18-26.** The age range of 18-26 (a) coincides with the distinct developmental period of “emerging adulthood” (Arnett, 2005), (b) is characterized by a high prevalence of heavy episodic drinking (Johnson et al., 2012), and (c) is representative of college students, the majority of whom are 26 years of age or younger (Digest of Education Statistics: 2012).

(2) Male or female student at Brown University or University of Houston. The present study represents a first step in using counter-attitudinal advocacy activities in an attempt to reduce risky drinking behavior. As such, we focus on college students because they exhibit high rates of heavy episodic drinking (Johnson et al., 2012), and their identification with other college peers facilitates the testing of the enhanced manipulation. We recruit at 2 sites that differ in drinking patterns and demographics and geographic location to evaluate the generalizability of the study findings. The findings could have implications for alcohol abuse prevention both with college students and young adults more broadly.

(3) Past month heavy episodic drinking (for men, ≥ 5 drinks in one day, for women ≥ 4 drinks in one day). The 4/5 drink cutoff has been widely used as an indicator of risk ([name], Larimer, & Lewis, 2004; Wechsler & Nelson, 2001) and as a screening criterion in intervention studies targeting heavy drinking students. Our preliminary studies show that heavy drinking frequency is significantly correlated with attitudes towards moderate ($r = -.42$) and heavy ($r = .45$) drinking. By including only drinkers who have reported heavy episodic drinking we optimize the likelihood that developing arguments in favor of moderate drinking ($<4/5$ drinks/occasion) will constitute counter-attitudinal advocacy, and create dissonance between the espoused attitude in favor of moderation and recent behavior.

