13. Provide the analysis plan including the power calculation(s). There should be discussion of any planned interim and/or futility analyses, including adjustments for allocating “alpha” on “multiple looks” at the data.

Sample size and power calculations. Power analyses focus on estimating a sample size large enough to detect “true” effects, thereby avoiding Type II errors. Sample size estimates were obtained for intervention contrasts. Necessary sample sizes were assessed via sample size and power equations for multi-level models using the Optimal Design software program.

Based on previous findings using CAA and PNF approaches, we anticipate intervention effects relative to the neutral control condition to be in the small to medium range but at least comparable to effects which have been reported for personalized normative feedback, which are typically in the .28 range (e.g., Dotson et al., 2015). Based on the proposed sample size of 600, given four assessment points, we anticipate the ability to detect effects of intervention contrasts and moderation effects across the small to medium range.

Considering maximum anticipated attrition rates of 15% (N=510) we will have .70, .80, and .90 power to detect effects sizes of delta = .24, .27, and .32, respectively.

14. Provide the study stopping rules part of the study protocol. Generally, stopping rules reflect one of the following conditions: 1) there is clear evidence of harm; 2) there is no likelihood of demonstrating treatment benefit (futility); 3) there is overwhelming evidence of the benefit of treatment.

There are no study stopping rules associated with the current protocol. Based on prior research, there is no reason to believe that the interventions used in this study could cause harm. Therefore, we do not plan interim analyses prior to achieving our full sample. We anticipate that the full sample will be needed to have sufficient power to detect significant group differences.

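### The power statement for moderation does not hold for study site, so a non-significant site interaction cannot show that the CAA effect is the same at both campuses

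*Combined protocol and SAP*

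**What the plan says.** Section 4, Aim 4a, predicts that the CAA effect "will not differ by study site". Aim 4b predicts a site difference for PNF, whose effect "will be stronger within a lighter drinking community (the Houston site)"; no size is given. Section 5 explains the choice of two contrasting campuses and adds: "If site does not moderate efficacy, then the replication of the effects of CAA across sites will provide evidence of generalizability of observed effects".

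Section 10.1 makes one power statement for main contrasts and moderation together: "we anticipate the ability to detect effects of intervention contrasts and moderation effects across the small to medium range". The only numbers behind it are in the next sentence, "Considering maximum anticipated attrition rates of 15% (N=510) we will have .70, .80, and .90 power to detect effects sizes of" .24, .27 and .32. DSMP item 13 (Appendix E) repeats both statements.

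Under Section 10.2, the Aim 4 analysis adds the moderators and their products with the condition contrasts to the model. The documents give no bound on the site difference, no criterion for replication and no power figure specific to an interaction. For Aim 2, by contrast, the plan does set numerical margins for its claim that CAA is not worse than PNF.

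**The concern.** Aim 4a is a prediction of no difference, tested with a method designed to detect a difference. Failing to find one is informative only if the test had a good chance of finding a difference that matters. Section 10.1 suggests that it has, but a site-by-condition contrast compares two half-sized contrasts and is much less precise than the pooled comparison to which the stated figures apply.

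At stake is the purpose of the two-site design. CAA could help at one campus and not at the other and still, more often than not, give a non-significant interaction. If that result were reported as agreement between sites, a campus deciding whether to adopt CAA would be relying on a comparison that could not have answered its question.

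**Working it through.** **Inputs.** Section 6.1: "We will randomize 100 eligible students from each site to the CAA" condition, and likewise to PNF and AO, so 200 per arm and 600 in all. Section 10.1: 15% attrition, N = 510, hence 170 per arm and, if losses are even, 85 per arm per site. Expected effects against control are those for PNF, "which are typically in the .28 range". Alpha, sidedness and within-person correlation are not stated. I assume alpha .05, try both one- and two-sided tests, and take delta as a standardised difference (SD = 1).

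**1. Reproducing the stated power.** For a pooled two-arm contrast with 170 per arm, SE = sqrt(2/170) = .1085.

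| Calibration | .24 | .27 | .32 |
|---|---|---|---|
| Stated | .70 | .80 | .90 |
| Two-sided, single measure | .600 | .702 | .839 |
| One-sided, single measure | .715 | .801 | .904 |
| Two-sided, mean of 4 assessments, assumed correlation .72 | .702 | .800 | .913 |

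The last two rows match within 2 percentage points. The stated figures are therefore those of a pooled contrast, with either a one-sided test or a repeated-measures gain that the plan does not describe. On the two-sided reading, the implied SE is .27/(1.960 + .842) = .0964.

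**2. SE of the site contrast.** Each site-specific contrast has half the participants, so its variance is twice the pooled variance V. The difference between two such contrasts has variance 2V + 2V = 4V, and its SE is twice the pooled SE. As a check, sqrt(4/85) = .217 = 2 × .1085. This ratio does not depend on alpha, sidedness or correlation. It assumes equal precision at the two sites; with unequal precision and inverse-variance pooling, it exceeds two.

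**3. Detectable site difference.** Doubling the stated values gives .48, .54 and .64 at .70, .80 and .90 power. At 80% power under each calibration:

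- two-sided, implied SE: 2.802 × .193 = .54
- one-sided, single measure: (1.645 + .842) × .217 = .54
- two-sided, single measure (does not reproduce the stated power): 2.802 × .217 = .61

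**4. Power for a given site difference d**, as Phi(d/SE − z):

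| d | Two-sided, SE .193 | Two-sided, SE .217 | One-sided, SE .217 |
|---|---|---|---|
| .20 | .18 | .15 | .24 |
| .28 | .31 | .25 | .36 |
| .50 | .74 | .64 | .75 |

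A difference of .28 is missed 64% to 75% of the time.

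**5. What the interval can exclude.** The 95% CI half-width is 1.96 × .193 = .38 to 1.96 × .217 = .43. Since this exceeds .28, the interval extends beyond .28 in at least one direction whatever the estimate. An observed difference of exactly zero would still leave true differences up to about .38 to .43 inside it.

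**6. Replication read as significance at each site.** The site-specific SE is sqrt(2) × .0964 = .136, or sqrt(2) × .1085 = .153. With a true effect of .28 at both sites, power per site is .54 (two-sided, .136), .45 (two-sided, .153) or .57 (one-sided, .153). Both sites are significant in .29, .20 and .33 of trials respectively.

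**The case against.** **Section 5 asks for more than a null interaction.** A reader might infer that the plan takes non-significance alone as proof of generalizability. It does not: the sentence also requires the CAA effect to be replicated across sites. If that means significance at each site, and the true effect is .28 at one campus and zero at the other, both sites would be favourably significant only about .54 × .025 = 1.3% of the time (two-sided) or .57 × .05 = 2.9% (one-sided). On that reading false claims are rare, and the weakness is failing to confirm a real common effect (step 6). This objection stands as far as it goes. But the criterion is not stated, and a pooled effect with a null interaction would also fit the wording. Aim 4a's prediction does not mention replication at all.

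**The moderation statement is qualitative and covers several moderators.** A reader might infer that power is short for all of them. The documents do not support that. For a continuous moderator (drinker identity, preference for consistency), an interaction expressed per SD has about the same SE as the main contrast.

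**Small to medium reaches .50.** Power there is 64% to 75%, so the gap is worst for smaller differences. Nor can one say that the test would miss most plausible site differences, because the documents give no size for any.

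**A more efficient analysis could do better.** Analysis of covariance on the mean of three follow-ups, with an assumed correlation of .6, has variance factor (1 + 2 × .6)/3 − .36 = .373. The interaction SE is then .217 × sqrt(.373) = .133, the difference detectable at 80% power is .37, and power at .28 is 56%. That still misses 44%, and it implies main-contrast power of about .98 at .27 where the plan states .80, so it is not the plan's own scenario.

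**Consequence.** Site moderation belongs to Aim 4, and the Section 5 sentence is design rationale, not a formal decision rule.

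**Conclusion.** The concern holds for the site moderator. The plan's own power figures imply a detectable site difference of about .54 at 80% power (.54 to .61 across the assumptions tried) and 25% to 36% power for a difference as large as the whole expected effect. The statement that moderation is detectable across the small to medium range is therefore not met for site. A non-significant interaction cannot support Aim 4a's prediction, nor the Section 5 conclusion while replication remains undefined.

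The factor of two rests on equal sites and even losses. The power percentages also rest on alpha .05, an assumed sidedness and a standardised delta. The result does not extend to the continuous moderators and does not touch Aims 1 or 2.

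**What to change.** 1. **Section 10.1 and DSMP item 13.** Limit the small-to-medium statement to the main contrasts. State the detectable site-moderation effect as about .54 at 80% power, and give the alpha, sidedness and within-person correlation behind all the figures. If a statement is wanted for the continuous moderators, give it separately with the effect scale defined.
2. **Section 5 and Aim 4a.** Base the conclusion on the site-specific CAA versus AO effects and the site × CAA × Time estimate, each with a 95% CI, and say what counts as replication. State that a non-significant interaction is not evidence of similarity. Call the comparison inconclusive when the interval includes both zero and a difference as large as the expected effect (about .28). Because the Section 10.2 model has a log link, say how .28 translates to its scale.
3. **Say in advance that inconclusive will be the usual result.** With a half-width of .38 to .43, similarity within .28 cannot be shown at this size. An equivalence margin would not rescue the claim: even a 90% CI has half-width 1.645 × .193 = .32 to 1.645 × .217 = .36, and 80% power for equivalence with no true difference needs a margin of about .56 to .63. Testing a .28 interaction with 80% power would take roughly 1,900 to 2,400 analysed participants (510 × (.54/.28)² to 510 × (.61/.28)²), so a larger trial is not the suggestion.

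The cost is a less favourable stated figure and a more cautious conclusion on generalizability. No extra data or participants are needed.
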